7.2. BACKGROUND ON THE MOLECULE

7.3. RATIONALE FOR DOING THIS STUDY

7.4. DOSING REGIMEN AND STARTING DOSE

CX-4945 will be administered twice a day on a continuous basis. Each cycle will be 28 days (4 weeks) in duration and the first cycle will be used as the DLT observation period.

The starting dose will be 1000 mg BID (2000 mg total daily dose). This starting dose is based on three completed Phase I studies where patients were administered CX-4945 following a twice-daily (BID) or four-times-daily (QID) dosing regimen for 21 days followed by 7 days of rest. A total of 12 patients were treated at the 1000 mg bid dose level. Grade 3 or greater hypokalemia and hyponatremia associated to CX-4945 were reported but no drug-related severe diarrhea was noted. At the 1000 mg bid dose level, 1 out of 12 patients had DLT, grade 4 hypokalemia.

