11.6. DOSE MODIFICATION FOR CX-4945

The most common drug related adverse events reported for CX-4945 are predominantly gastrointestinal disorders, including nausea, vomiting and diarrhea.

| Toxicities related to CX-4945 | | | | | | | |
|-------------------------------|----------------------|--|--|--|--|--|--|
| Event Grade (CTCAE 5.0) | Dose Interruption | Dose Reduction | Dose for subsequent cycle | | | | |
| Grade 1 | Treat on time | No change | No change | | | | |
| Grade 2 | Hold until ≤ Grade 1 | Resume at same dose | No change | | | | |
| Grade 3 | Hold until < Grade 2 | Reduce by 1 dose level (200 mg) | If toxicity remains <grade 2, dose re-escalation can be considered at the discretion of the Investigator. If dose is re-escalated and toxicity (≥ Grade 3) recurs, institute permanent dose reduction.</grade | | | | |
| Grade 4 | Hold until < Grade 2 | Reduce by 1 dose level (200 mg). Permanent discontinuation can be considered at the Investigator's discretion | | | | | |

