16.3. PROCEDURES FOR RECORDING ADVERSE EVENTS

16.3.1. Recording Adverse Events on the eCRF

Investigators should use correct medical terminology/concepts when recording AEs or SAEs on the eCRF and should avoid colloquialisms and abbreviations. Only one medical concept should be recorded in the event field on the AE/SAE eCRF page.

A. Diagnosis versus Signs and Symptoms

If known, a diagnosis should be recorded on the eCRF rather than individual signs and symptoms (e.g., record only liver failure or hepatitis rather than jaundice, asterixis, and elevated transaminases). However, if a constellation of signs and/or symptoms cannot be medically characterized as a single diagnosis or syndrome at the time of reporting, each individual event should be recorded as an AE or SAE on the eCRF. If a diagnosis is subsequently established, it should be reported as follow-up information.

B. Adverse Events Occurring Secondary to Other Events

In general, AEs occurring secondary to other events (e.g., cascade events or clinical sequelae) should be identified by their primary cause. For example, if severe diarrhea is known to have resulted in dehydration, it is sufficient to record only diarrhea as an AE or SAE on the eCRF.

However, medically significant AEs occurring secondary to an initiating event that are separated in time should be recorded as independent events on the eCRF. For example, if a severe gastrointestinal hemorrhage leads to renal failure, both events should be recorded separately on the eCRF.

C. Persistent or Recurrent Adverse Events

A persistent AE is one that extends continuously, without resolution between patient evaluation timepoints. Such events should only be recorded once on the eCRF unless their severity increases. If a persistent AE becomes more severe, it should be recorded again on an AE/SAE eCRF.

A recurrent AE is one that occurs and resolves between patient evaluation timepoints and subsequently recurs. All recurrent AEs should be recorded on an AE/SAE eCRF.

D. Abnormal Laboratory Values

Only clinically significant laboratory abnormalities that require active management will be recorded as AEs or SAEs on the eCRF (e.g., abnormalities that require study drug dose modification, discontinuation of study treatment, more frequent follow-up assessments, further diagnostic investigation, etc.).

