Adverse event terms will be coded using Medical Dictionary for Regulatory Activities (MedDRA) dictionary. A treatment-emergent AE (TEAE) is defined as an AE that starts or worsen on or after the date of the first dose of study medication. Adverse events that have missing onset dates will be considered to be treatment emergent, unless the stop date is known to be prior to the first administration of the study medication. If the AE onset date is partial, the date will be compared as far as possible with the date of first dose of study medication. Adverse events will be assumed to be treatment-emergent, unless there is clear evidence (through comparison of partial dates) to suggest that the AE started prior to the first dose of study medication. All TEAE swill be mapped to thesaurus terms and graded according to the NCI CTCAE, version 5.0.

All AEs will be listed by subject, detailing the verbatim term given by the investigator, the preferred term (PT), system organ class (SOC), onset date, end date, CTCAE Grade, outcome, relationship to study drug, action taken with study drug, other action taken, seriousness and criteria for seriousness. Serious AEs (SAEs) and TEAEs leading to study discontinuation will also be listed separately.

The following TEAE summaries will be produced by cohort (treatment-duration-increment, expansion) and overall:

- An overall summary of safety will summarize the numbers (and percentages) of patients with the following:
 - Any TEAEs and serious adverse event (SAE)
 - AEs related to study drug
 - SAEs related to study drug
 - AEs of Clinical Interest
 - DLTs
 - Who discontinued study drug due to at least one AE (regardless of causality, and related to each study drug)
 - AEs leading to death
- Separate summaries of TEAEs by SOC and PT, subset as follows:
 - All AEs
 - AEs related to study drug. Related AEs will include AEs with a drug relationship of "Related" recorded on CRF.
 - All SAEs
 - SAEs related to study drug
 - All Grade 3 or above AEs

- Grade 3 or above AEs related to study drug
- All AEs in at least 10% of subjects
- AEs in at least 10% of subjects related to study drug
- All AEs leading to discontinuation of study drug
- All AEs leading to dose interruptions
- All AEs leading to dose modifications
- All AEs leading to death, overall, while on study and during the 3-month followup period
- All AEs by SOC, PT and CTCAE toxicity grade
- All AEs by SOC, PT and action taken with study drug
- All AEs by PT

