If a patient has multiple occurrences of an AE, the strongest level of relationship to study drug and the worst toxicity grade a patient experiences for a given AE will be used in these tables. Further, if the toxicity grade is missing, the event will be reported as 'unknown' in the summary tables. Likewise, if causality data is missing, 'unknown' will be reported.

11.11.4Clinical Laboratory Testing

Clinical laboratory values will be reported as complete listings of individual subject data. All laboratory values will be classified as normal, low, or high based on normal ranges supplied by the laboratory. Clinical laboratory values outside of normal range will be listed in a separate by-subject listing.

Absolute values and changes from baseline of clinical laboratory data (hematology, chemistry, and continuous urinalysis parameter) will be summarized descriptively. Changes in out-of-range reference flags from Baseline to post-baseline visits in clinical laboratory data will also be summarized using shift tables.

Vitamin D assessments, pregnancy test results will be presented in separate by-subject listings.

11.11.5Vital Signs

Vital signs including body weight, blood pressure (systolic and diastolic), pulse rate, respiratory rate, and body temperature will be presented in a by-subject listing by visit. Absolute values and change from baseline value will be summarized by treatment group using descriptive statistics.

11.11.6Electrocardiogram (ECG)

ECG data measured at Screening will be presented in a by-subject listing.

11.11.7Physical Examination

Physical examination results will be captured on eCRF but will not be presented in tables or listings.

11.11.8ECOG Performance Status

The Eastern Cooperative Oncology Group (ECOG) status of patients will be listed and summarized using frequency counts and percentages by visit.

12.CHANGES FROM THE PROTOCOL AND PLANNED ANALYSES

This SAP reflects the analysis plan outlined in the study protocol without significant change. Any analysis changes or additional analysis not specified in this SAP will have the status of unblinded and exploratory investigations.

13.HEADINGS

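### SAP 11.11.4 plans no CTCAE-graded laboratory summary, so Grade 3-4 hypokalemia and hyponatremia can be checked against the AE and DLT tables only by hand

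*SAP*

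**What the plan says.** SAP 11.11.4 (Clinical Laboratory Testing) gives the classification rule: "All laboratory values will be classified as normal, low, or high based on normal ranges supplied by the laboratory". On shifts it says: "Changes in out-of-range reference flags from Baseline to post-baseline visits in clinical laboratory data will also be summarized using shift tables". It also plans complete listings of individual values, a separate by-subject listing of out-of-range values, and descriptive summaries of values and changes. Under SAP 10.1 those summaries include minimum and maximum.

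CTCAE grading enters the SAP through adverse events. Section 11.11.3 has treatment-emergent AEs "graded according to the NCI CTCAE, version 5.0", with tables of Grade 3 or higher events, all and drug-related. Section 11.11.2 defines DLTs by the grade of drug-related AEs in Cycle 1, which it takes as 28 days of dosing.

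Protocol 7.4 describes the earlier experience: "Grade 3 or greater hypokalemia and hyponatremia associated to CX-4945 were reported but no drug-related severe diarrhea was noted". It adds: "At the 1000 mg bid dose level, 1 out of 12 patients had DLT, grade 4 hypokalemia".

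Protocol 16.3.1 D makes a laboratory abnormality an AE only if it is clinically significant and needs active management. Its examples include "abnormalities that require study drug dose modification", closer follow-up and further investigation.

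**The concern.** A low/normal/high flag does not carry severity. A potassium value just under the range and one low enough to be dose limiting fall in the same shift-table cell. The toxicity that was dose limiting before is an electrolyte abnormality, and this study gives the same dose without the 7-day rest.

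Safety and tolerability are a secondary objective. Without a graded laboratory table, the only planned counts of severe electrolyte toxicity come from AE records, and those depend on the investigator's judgement of clinical significance, primary cause and, for some tables, relatedness. A count derived from the numeric values needs none of these judgements and could support or question the AE tables.

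**Working it through.** The plan states no figure on this point, so the check is mainly a comparison of sections.

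**1. What the flag table can show.** Assume, for illustration only, a potassium reference range of 3.5 to 5.0 (not in the documents). Four values of 3.4 and four values of 2.0 are all flagged low and share a cell. The minimum separates the two sets (3.4 against 2.0); the flag does not.

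**2. What the other planned laboratory outputs add.** The minimum gives the lowest value in a group, not how many patients reached Grade 3-4. The listings contain the individual values but leave grading and counting to the reader. SAP 10.4 summarises by the visit recorded in the eCRF, without windows, and the SAP does not say whether unscheduled values enter the summaries.

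**3. How a Grade 3-4 value reaches the AE tables.**

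| Investigator's judgement | Rule | Result |
|---|---|---|
| Related | Protocol 11.6, in its table headed "Toxicities related to CX-4945", requires a hold and, as the default, a dose reduction at Grade 3 or 4; 16.3.1 D lists dose modification as a ground for recording | Should be in the AE tables, and in the DLT table if in Cycle 1 and the definition is met |
| Unrelated, but actively managed | Protocol 16.2.1 collects AEs whatever their attribution; SAP 11.11.3 tabulates all Grade 3+ AEs | In the all-cause Grade 3+ table; absent from the related-AE and DLT tables |
| Not clinically significant | 16.3.1 D does not record it | In no AE table |
| Secondary to another event | 16.3.1 B generally records the primary cause, but records medically significant secondary events separated in time | May be absent when it follows closely on, say, vomiting |

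On the last row, Protocol 11.6 describes the commonest drug-related events as "predominantly gastrointestinal disorders, including nausea, vomiting and diarrhea". The group may still be small, since 7.4 reports no severe drug-related diarrhea.

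**4. Size.** The only documented rate is 1/12 = 8.3%, exact (Clopper-Pearson) 95% CI 0.2% to 38.5%, on the 21-days-on, 7-days-off schedule. It counts a DLT that was recognised and recorded. It says nothing about the frequency of unrecorded values.

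**5. Cycle 1 timing.** Appendix A schedules serum chemistry at screening and every 4 weeks (±3 days), with none on Day 1. One scheduled post-baseline draw therefore relates to Cycle 1.

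- If it is the Cycle 2 Day 1 visit: 29 ± 3 = Days 26 to 32. Days 29 to 32 are after Day 28, which is 4 of 7 window days.
- If it is Day 28: 28 ± 3 = Days 25 to 31. Days 29 to 31 are after Day 28, which is 3 of 7.

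Any comparison with DLTs thus needs the study day of each value, and unscheduled draws matter.

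**The case against.** The strongest reply is that the SAP already lets a reader make the check. Values are listed in full, out-of-range values are listed again, AE listings carry onset date, grade and relatedness, and DLTs are listed. The study is small: SAP section 6 reports only 2 metastatic patients enrolled in the expansion. Assuming a full run-in of 6, a full locally advanced cohort of 10 and no replacements, the total is 6 + 10 + 2 = 18. Matching by hand is feasible at that size. This stands, and it defeats the inference a reader might draw that the SAP has no laboratory-based cross-check. What is missing is a tabulated, graded one.

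Other safeguards also count. Recording under 16.3.1 D is triggered by closer follow-up or further investigation as well as by dose changes. The mention in Protocol 9.4 of abnormalities judged not clinically significant concerns which events are intolerable; it is not a recording rule. Protocol 17.6 asks the investigator to comment on markedly abnormal values, and section 18 plans full source verification. These narrow the routes by which a value is lost but do not produce a count.

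SAP section 12 gives exploratory status to analyses added later. That costs little here, because SAP 10.5 plans no formal testing. The better reason to act early is that unmatched values can be queried before closure; under SAP section 5, later database changes need written authorisation.

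**Conclusion.** The point holds as a reporting weakness that is cheap to repair. No planned laboratory table counts patients with Grade 3-4 hypokalemia or hyponatremia, and severity can be compared with the AE and DLT tables only by hand from the listings and the minimum and maximum values.

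The documents do not support three stronger readings:

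- That severe values are probably missing from the AE tables. Most should reach them, and the size of any under-count is unknown.
- That the SAP departs from the protocol. Protocol 15.1 promises summaries of laboratory results and does not require grading.
- That the dose recommendation is in doubt. It is set during the study by the rules in Protocol 9.1, not by these tables.

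The conclusion concerns the outputs named in the SAP. Reconciliation of laboratory and AE data may be planned in data-review documents that are not available here.

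**What to change.** In SAP 11.11.4:

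- Derive CTCAE v5.0 grades from the numeric potassium and sodium results, ideally for all gradable analytes. State the rule for any grade that does not rest on the number alone.
- Tabulate baseline grade against worst post-baseline grade, including unscheduled values, by cohort and overall, in place of or beside the flag shift tables.
- List each Grade 3-4 value with its study day beside any matching AE term, grade, relatedness and DLT flag. Mark values after Day 28 as outside the DLT window, so that a draw at the Cycle 2 visit is not read as a missed DLT.
- Query unmatched values before database closure (SAP section 5).

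The cost is one derivation, one or two tables and one listing, from chemistry data already collected, with no new patient procedures. The downside is extra programming and possibly a few late queries or AE corrections. The outputs can show only values that were drawn.
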